10.4.2 Concomitant medication

Concomitant medication will be coded using the World Health Organization drug dictionary (version is documented in the DMP). Concomitant medication will be listed.

10.4.3 Clinical laboratory parameters

All clinical chemistry and hematology data will be summarized by time point, and listed. Urinalysis data will be listed. Additionally, clinical chemistry, hematology and urinalysis data outside the reference ranges will be listed and flagged on individual participant data listings.

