7.2. Participant Discontinuation/Withdrawal from the Study

Discontinuation is expected to be uncommon.

A participant may withdraw from the study:

- at any time at the participant's own request
- at the request of the participant's designee (eg, parents or legal guardian)
- at the discretion of the investigator for safety, behavioral, compliance, or administrative reasons

- if enrolled in any other clinical study involving an investigational product, or enrolled in any other type of medical research judged not to be scientifically or medically compatible with this study
- if the participant, for any reason, requires treatment with a therapeutic agent that is prohibited by the protocol and has been demonstrated to be effective for treatment of the study indication. In this case, discontinuation from the study occurs prior to introduction of the new agent.

At the time of discontinuing from the study, if possible, the participant will complete procedures for an early discontinuation visit, as shown in the SoA. If the participant has not already discontinued the study intervention, the participant will be permanently discontinued from the study intervention at the time of the decision to discontinue the study.

If the participant withdraws consent for disclosure of future information, the sponsor may retain and continue to use any data collected before such a withdrawal of consent. If a participant withdraws from the study, the participant may request destruction of any samples taken and not tested, and the investigator must document this in the site study records.

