8. SAMPLE SIZE JUSTIFICATION

Approximately 40 participants may be enrolled so that approximately 25 participants complete the study. The sample sizes described are customary for Phase 1 studies evaluating safety, PK, and immunogenicity and is not powered on the basis of statistical hypothesis testing.

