10. STATISTICAL METHODOLOGY

10.1 General

Data listings will be provided for all data that is databased. Summary statistics and statistical analysis will only be presented for data where detailed in this SAP. For continuous data, summary statistics will include the arithmetic mean, arithmetic standard deviation (SD), median, minimum, maximum and number of observations; for log-normal data (e.g. the PK parameters: area under the concentration versus time curve [AUCs] and maximum observed drug concentration [C_{max}]) the geometric mean and geometric coefficient of variation (CV%) will also be presented. For categorical data, frequency count and percentages will be presented. Data listings will be provided for all participants up to the point of withdrawal, with any participants excluded from the relevant population highlighted. Summary statistics and statistical analyses will generally only be performed for participants included in the relevant analysis population. For the calculation of summary statistics and statistical analysis, unrounded data will be used.

For change from baseline summary statistics, each individual change from baseline will be calculated by subtracting the individual participant’s baseline value from the value at that time point. The individual participants’ change from baseline values will be used to calculate the summary statistics (arithmetic mean, arithmetic SD, median, minimum, maximum and number of observations) using a SAS procedure such as Proc Univariate.

Data analysis will be performed using SAS® Version 9.4 or greater.

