10.4.4 Vital signs

Vital signs data collected during the treatment periods will be summarized by time point together with changes from baseline, where baseline is defined as the Day 1 pre-dose assessment in each treatment period. Figures of mean vital signs and mean changes from baseline profiles will be presented by treatment.

Values for individual participants will be listed.

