10.4.13 Safety and Tolerability Statistical Methodology

No inferential statistical analyses are planned.

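### Laboratory tables give raw values by time point only, with no baseline, change from baseline or shift table, so within-participant shifts inside the reference range are not tabulated

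*SAP*

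**What the plan says.** SAP 10.4.3 gives the whole plan for laboratory tables in one sentence: "All clinical chemistry and hematology data will be summarized by time point, and listed". It then adds that "clinical chemistry, hematology and urinalysis data outside the reference ranges will be listed and flagged on individual participant data listings". It mentions no baseline, change from baseline or shift table.

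SAP 10.1 describes how an individual change from baseline is computed and summarised, but it also limits the outputs: "Summary statistics and statistical analysis will only be presented for data where detailed in this SAP". The change-from-baseline method therefore applies only where a later section calls for it. SAP 10.4.4 does so for vital signs, which are to be "summarized by time point together with changes from baseline", with a stated baseline. SAP 10.4.7 also names a baseline for anti-drug antibodies, the Day -1 sample of Treatment Period 1. The laboratory section names none.

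On numbers, SAP 8 states: "Approximately 40 participants may be enrolled so that approximately 25 participants complete the study". Protocol 7.2 states: "Discontinuation is expected to be uncommon". The study is "not powered on the basis of statistical hypothesis testing", and for safety SAP 10.4.13 says "No inferential statistical analyses are planned".

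**The concern.** There is no control arm. Apart from fixed reference ranges, the only comparison available for laboratory safety is each participant against his or her own pre-dose value, and the planned tables do not make it. The protocol itself treats that comparison as meaningful: several liver criteria in Protocol 7.1.1 and 8.2.8.1 are multiples of baseline when the baseline is raised, and Protocol 8.2.4 has abnormal tests repeated until they return to normal or baseline.

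Two things are at stake, both descriptive. A consistent change that stays inside the reference range would have to be found by reading listings. And a difference between an early and a late raw mean mixes change within people with change in who is still being measured.

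**Working it through.** **1. Are the data there?** The schedule in Protocol 1.3 has a laboratory panel on Day -1 and at 24 hours in each of 6 periods, plus one at Day 96: 6 × 2 + 1 = 13. Protocol 10.2.1 also counts 13. Taking Period 1 Day -1 as baseline leaves 13 − 1 = 12 later panels.

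**2. What do raw tables lose even if nobody leaves?** With the same people at both visits, the difference of two raw means equals the mean change, so a group mean shift can be recovered. Its spread cannot. In units of the between-person SD, the SD of change is √(2(1 − ρ)), where ρ is the within-person correlation. The tables do not give ρ, and neither do the documents. For assumed ρ of 0.5, 0.7, 0.8 and 0.9, the SD of change is 1.00, 0.77, 0.63 and 0.45. Nor does the mean reveal one person's change: a single 3 SD rise moves a mean of 25 by 3/25 = 0.12 SD.

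**3. How much do the out-of-range flags catch?** Assume a reference range of mean ± 1.96 SD and a participant starting at random inside it. The chance that a rise of r SD stays in range, and so unflagged, is [Φ(1.96 − r) − 0.025]/0.95.

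| Rise | Unflagged |
|---|---|
| 1 SD | 85% |
| 2 SD | 48% |
| 3 SD | 13% |

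The listings do hold these values. Protocol Appendix 2 names 13 haematology and 17 chemistry analytes, so 30 × 13 = 390 values per completer and 390 × 25 = 9,750 for 25 completers.

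**4. How far can the raw mean move because people leave?** The documents state no dropout rate to reproduce. The two approximate figures give 40 − 25 = 15, and 15/40 = 37.5%. If m of 40 have left before a panel, and leavers differ from stayers by d SD at baseline, the mean moves by d × m/40 with nobody changing. The values of d are assumptions.

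| Leavers m | d = 0.25 | d = 0.50 | d = 0.75 |
|---|---|---|---|
| 15 | 0.094 | 0.188 | 0.281 |
| 4 | 0.025 | 0.050 | 0.075 |

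For scale, the standard error of a mean of 25 is 1/√25 = 0.20 SD. If 15 leave purely at random, the shift is centred on zero with SD √(1/25 − 1/40) = 0.12.

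**5. Does change from baseline cure it?** This was simulated with 20,000 trials of 40, 25 retained and no true drug effect, with higher values more likely to leave. The correlation between dropout and baseline was 0.3 or 0.5. At 15 leavers these correspond to d of about 0.177/0.375 = 0.47 and 0.298/0.375 = 0.8.

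| ρ | Dropout correlation | Raw mean shift | Paired change, same 25 |
|---|---|---|---|
| 0.9 | 0.3 | −0.16 | +0.02 |
| 0.9 | 0.5 | −0.27 | +0.03 |
| 0.7 | 0.3 | −0.13 | +0.05 |
| 0.7 | 0.5 | −0.21 | +0.09 |
| 0.5 | 0.3 | −0.09 | +0.09 |
| 0.5 | 0.5 | −0.15 | +0.15 |

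Paired change helps when analytes are stable within a person. At ρ = 0.5 it has no advantage, because regression to the mean replaces the composition effect.

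**The case against.** A reader might infer that real individual changes are hidden. The documents do not support that. All values are listed, out-of-range values are flagged by participant, and SAP 10.1 gives minimum, maximum and n at each time point. Protocol 8.2.4 requires clinically relevant laboratory changes to be reported as AEs, and SAP 10.4.6 has separate hepatic outputs. What is left untabulated is movement inside the range.

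A reader might also infer that 37.5% dropout is planned and that it will distort the means. That is not supported either. The 15 comes from two approximate numbers and is neither a stated rate nor a ceiling; Protocol 7.2 points to fewer. Non-completion is also not the same as missing laboratory data. Under Protocol 4.4 someone who misses only the last visit is a non-completer, yet can supply 12 of 13 panels. Under Protocol 7.1 a participant who stops dosing stays for the remaining visits, and the schedule appears to include a panel at early discontinuation. So the d × 15/40 figures are a worst case. No mechanism linking dropout to laboratory values is evident in healthy adults aged 18 to 40, and the n shown at each time point would warn the reader.

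Finally, there is no conflict with the protocol. Protocol 9.3.5.2 asks only for listings and standard descriptive statistics, laboratory values are not an endpoint, and both documents allow further analyses. The separate table shells, which may hold more, are not available here.

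All of this stands as a limit on size. It does not supply the missing comparison. AE reporting depends on judging one participant at a time, so it would not bring out a modest shift across the group. An analysis added after review of the data is not prespecified.

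**Conclusion.** The point holds as a minor one. The laboratory tables contain no within-participant comparison, although the baseline sample is scheduled, the method is in SAP 10.1, and vital signs already use it. This does not depend on any dropout rate.

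The effect of a changing set of participants is possible but of unknown size. It is 0.09 to 0.28 SD if all 15 implied leavers were gone before the panel, and 0.025 to 0.075 SD with 4 gone, in both cases assuming that leavers differ by 0.25 to 0.75 SD. The SDs, the within-person correlation and the link between dropout and laboratory values are all assumptions. Because safety analysis is descriptive, no error rate is involved, and no primary pharmacokinetic result changes.

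**What to change.** In SAP 10.4.3:

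- Define laboratory baseline as the Treatment Period 1 Day -1 value. One fixed pre-dose baseline lets change be followed across all six doses; a baseline reset each period, as for vital signs, would not.
- Add change from baseline by time point, with n, for chemistry and haematology, using the method in SAP 10.1.
- Add a low/normal/high shift table from baseline, including the worst post-baseline value (the highest and the lowest where both directions matter).

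The cost is two more table types from samples already scheduled. Two limits should be understood. Paired change reduces the effect of selective dropout without removing it, and it does not remove regression to the mean. The shift table, through the worst post-baseline value, uses data from anyone with at least one later panel, including those who leave, but it records only moves across a range limit. The two tables are therefore needed together.

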10.4.4 Vital signs

Vital signs data collected during the treatment periods will be summarized by time point together with changes from baseline, where baseline is defined as the Day 1 pre-dose assessment in each treatment period. Figures of mean vital signs and mean changes from baseline profiles will be presented by treatment.

Values for individual participants will be listed.

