5. STUDY DESIGN

This is a Phase 1, open-label study to evaluate the PK, safety, and tolerability of 350 mg donanemab administered as a single IV dose every 2 weeks (Q2W) for 10 weeks in healthy participants. Approximately 40 participants may be enrolled so that approximately 25 participants complete the study. Participants will receive a single 350 mg dose of donanemab Q2W for 10 weeks. After each dose administration, participants will remain in the clinical research unit (CRU) for up to 5 days. Participants will return to the CRU for regular outpatient visits until the next dose of donanemab. These visits will occur on Days 3, 4, 5, and 8 (unless the participant is still admitted to the CRU, in which activities for those days will be performed during the inpatient stay). After the last dose of donanemab, participants will return for outpatient visits up to 12 weeks after the last dose.

Screening may occur up to 28 days prior to enrollment into the study. Once the informed consent is signed by the participants, they will be assessed for eligibility and will undergo screening procedures.

[figure not shown]
Participants who are not enrolled within 28 days of screening may undergo an additional medical assessment and/or clinical measurements to confirm their eligibility. Eligible participants will be admitted to the CRU on Day -1 prior to dosing in each of the 6 treatment periods. On Day 1 of

each treatment period, participants will be dosed with an IV dose of donanemab and remain in the CRU until discharge on Day 2, although participants may remain inpatient up to Day 5 of each treatment period at the discretion of the investigator. After dosing with 350 mg donanemab, participants will return to the CRU approximately 2 weeks later to be admitted at Day -1 of the subsequent period.

Safety and tolerability will be assessed through electrocardiograms (ECGs), clinical laboratory tests, vital sign measurements, recording of adverse events (AEs), physical examination, and neurological examination. Additionally, immunogenicity will be assessed.

After discharge from the CRU after the final treatment period, participants will return for further outpatient assessments (safety, PK, and immunogenicity) until 12 weeks after the final dose.

Study Schema

Abbreviations: CRU = Clinical research unit

Figure 1: Illustration of Study Design for Protocol I5T-MC-AACP

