10.4.7 Immunogenicity Assessments

Immunogenicity data will be listed and frequency tables will be presented if analysed. The frequency and percentage of participants with pre-existing ADA and with TE ADAs will be presented. TE ADAs are those that are boosted or induced by exposure to study drug, with a 4-fold increase in titer compared to baseline if ADAs were detected at baseline or a titer 2-fold greater than the minimum required dilution (1:5 if no ADAs were detected at baseline, where baseline is defined as sample taken on Day -1 in Treatment Period 1.

The frequency and percentage of participants with neutralizing antibodies, if measured, may also be tabulated for participants with TE ADA.

To assess the relationship between the PK parameters and ADA, a box plot of CL_{ss} versus TE ADA status (TE ADA+ versus TE ADA-) will be presented. Scatter plots will be presented for the observed C_{trough} (y - axis) vs ADA titer (Day 15, 29, 43, 57, 71) also boxplot of individual CL_{ss} vs ADA titer. Additional analyses may be conducted, if appropriate.

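### The vital-sign baseline restarts at every dose, so no within-participant change from the untreated value is summarized

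*SAP*

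**What the plan says.** SAP 10.4.4 plans that "Vital signs data collected during the treatment periods will be summarized by time point together with changes from baseline", and specifies that "baseline is defined as the Day 1 pre-dose assessment in each treatment period". It adds: "Figures of mean vital signs and mean changes from baseline profiles will be presented by treatment". Individual values are listed. SAP 10.1 gives the calculation: subtract the participant's "baseline value from the value at that time point", then summarize the individual changes by mean, SD, median, minimum, maximum and number of observations.

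The design is repeated dosing. SAP 5 describes donanemab "administered as a single IV dose every 2 weeks (Q2W) for 10 weeks in healthy participants", with participants "admitted to the CRU on Day -1 prior to dosing in each of the 6 treatment periods". The Schedule of Activities (protocol 1.3) places vital signs on Day -1, at Day 1 pre-dose and 6 hours, at 24 hours, on Days 3 to 5, and at the follow-up visits on Days 37 and 96. A note there restricts temperature to screening and Day 1 pre-dose.

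The protocol defines no vital-sign baseline. For anti-drug antibodies the SAP uses one pre-treatment reference: in 10.4.7, "baseline is defined as sample taken on Day -1 in Treatment Period 1".

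**The concern.** The study has one arm and no placebo, so a participant's own value before the first dose is the only untreated reference inside the study. Under SAP 10.4.4 that value serves as baseline in Period 1 only. From Period 2 onward each change is measured from a value taken after earlier doses, so a sustained change in blood pressure or pulse drops out of the change summaries.

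Other safety measurements do not fill the gap. SAP 10.4.3 summarizes laboratory data by time point without asking for change from baseline, and SAP 10.4.5 does not present ECGs. Vital signs are the one continuous safety measure for which the SAP specifies a change from baseline, and that change does not refer back to the untreated state after Period 1. At stake is the completeness of the descriptive safety and tolerability results. The primary PK objective is not affected.

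**Working it through.** No figure in the plan depends on this definition, so there is none to reproduce. The check applies the SAP's own subtraction rule.

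**Inputs.** Baseline rule: SAP 10.4.4. Subtraction rule: SAP 10.1. Six periods, 14 days apart: SAP 5. Half-lives: protocol 4.3, about 4.7 days at 210 mg and below, and 11 days from 700 to 2800 mg; the 350 mg dose lies between these ranges. The documents give no vital-sign drift or SD, so any mmHg figure below is an assumption.

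**1. What is removed.** Let V(k,t) be the value in period k at time t.
- Change under the SAP: V(k,t) − V(k,pre)
- Change from the untreated value: V(k,t) − V(1,pre)
- Second minus first: V(k,pre) − V(1,pre)

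The SAP definition therefore omits exactly the shift present at the pre-dose assessment of period k, and nothing else.

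**2. Are later baselines on drug?** With a one-compartment linear model, the fraction of drug left after 14 days is r = 2^(−14/half-life).
- 4.7 days: r = 0.127; accumulation 1/(1 − r) = 1.15
- 11 days: r = 0.414; accumulation 1/(1 − r) = 1.71

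The Period 6 pre-dose concentration, as a fraction of the steady-state trough, is 1 − r^5. At 11 days this is 1 − 0.414^5 = 0.988, and at 4.7 days it is practically 1. Later baselines are on drug. That makes a carried-over effect possible but does not show that one exists.

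**3. Illustration with assumed effects (mmHg, Periods 1 to 6).**

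| Assumed pattern | Change under SAP baseline | Change from Period 1 pre-dose |
|---|---|---|
| Drift 1 per interval, no acute effect | 0, 0, 0, 0, 0, 0 | 0, 1, 2, 3, 4, 5 |
| Drift 2 per interval, no acute effect | 0, 0, 0, 0, 0, 0 | 0, 2, 4, 6, 8, 10 |
| Drift 1 plus constant acute effect of 2 | 2, 2, 2, 2, 2, 2 | 2, 3, 4, 5, 6, 7 |
| Drift 2 plus constant acute effect of 2 | 2, 2, 2, 2, 2, 2 | 2, 4, 6, 8, 10, 12 |
| No drift; acute effect grows, then resolves before next dose | 1, 2, 3, 4, 5, 6 | 1, 2, 3, 4, 5, 6 |

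Five intervals at 1 to 2 mmHg give 5 to 10 mmHg at Period 6 pre-dose, none of which enters the SAP change. The last row shows that a growing but transient response is kept in full.

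**4. What the other planned outputs show.** Observed means by time point, the mean plots and the listings all contain the drift. If the same participants contribute throughout, subtracting the Period 1 pre-dose mean from a later mean gives the mean change. It does not give the SD, minimum or maximum of the individual changes, which SAP 10.1 prescribes for change summaries. Large sustained shifts in a few participants can therefore sit inside an unremarkable mean and be found only by reading listings.

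**5. Temperature.** If the Day 1 column of the Schedule of Activities applies in all six periods, each scheduled on-study temperature is itself that period's baseline, and no scheduled value follows it within the period. A Period 1 baseline would give five changes (Periods 2 to 6). If the note means Period 1 only, neither definition gives any.

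**6. Follow-up.** SAP 10.4.4 covers data from the treatment periods. The schedule labels Days 37 and 96 as follow-up to Treatment Period 6. Those values are either outside the summaries or compared with Period 6 pre-dose. In neither case is return to the untreated level summarized.

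**The case against.** The case for leaving the plan alone has several parts, and most of it stands.

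- **Drift remains visible.** A reader might infer that a cumulative shift would appear as zero throughout the vital-sign output. The documents do not support that. SAP 10.4.4 also plans observed-value summaries, plots of mean vital signs and individual listings; only the change columns and change plots omit the shift.
- **Not every build-up is removed.** A reader might also infer that any effect growing over six infusions is lost. Only the part still present at the next pre-dose is.
- **Attrition.** SAP 8 says "Approximately 40 participants may be enrolled so that approximately 25 participants complete the study". It is tempting to read this as a forecast that the sample will shrink from 40 to 25, making raw means unusable. It is an enrolment allowance, and protocol 7.2 anticipates few discontinuations. Even if 15 of 40 left at random, an assumed between-person SD of 8 to 15 mmHg gives a composition error in the mean of SD × √(1/25 − 1/40), about 1.0 to 1.8 mmHg. If dropouts differed from completers by an assumed 5 to 10 mmHg, the mean would move by 15/40 of that, about 1.9 to 3.8 mmHg. The documents give no evidence of such selective dropout.
- **The within-period baseline has a purpose.** Infusion reactions are a named risk, and pre-dose, 6-hour and 24-hour readings suit an acute contrast. The antibody baseline in SAP 10.4.7 is not inconsistent with this, because treatment-emergent antibodies need a pre-exposure reference by definition.
- **Limited consequence.** The secondary endpoint is the incidence of adverse events. Clinically significant vital-sign findings are captured as adverse events (protocol 10.3.1), and SAP 10.4.13 plans no inferential safety analysis.

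What the objection does not answer is the missing distribution of within-participant change from the untreated value. Observed means do not supply it even with no dropout.

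**Conclusion.** The point holds in a limited form. By the SAP's own formula, the planned change-from-baseline results for vital signs describe within-period effects only, and any shift carried to the next pre-dose is taken out of them. No within-participant contrast with the pre-treatment value is summarized after Period 1, and temperature has no scheduled post-baseline value under the per-period definition (reading the Day 1 column as applying to all six periods).

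The size in mmHg is unknown. The 5 to 10 mmHg example rests on an assumed, steady, fully persistent shift of 1 to 2 mmHg per interval and shows the mechanism only; the documents report no cumulative effect on blood pressure or pulse. Because the observed values are tabulated, plotted and listed, this is a modest gap in a descriptive safety analysis. No study conclusion depends on it.

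**What to change.** In SAP 10.4.4, keep the within-period change for acute infusion effects. Add a second change, measured from the Treatment Period 1 Day 1 pre-dose value, for all later time points. Name explicitly the pre-dose values of Periods 2 to 6 and the follow-up visits, and apply the SAP 10.1 change statistics to it. Label the two baselines distinctly in the table and figure shells, and state that temperature is summarized against the Period 1 value only.

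The cost is one additional column or table and the matching plot. It needs no new data collection and no change to any clinical procedure or to the PK analysis.
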